There are currently two vaccines approved for COVID-19 in Canada.^{3,4} Despite this, effective treatments are still needed for COVID-19. It is anticipated to take approximately one year for Canadians to be vaccinated,⁵ the long-term efficacy of the approved vaccines are not yet known as median follow-up for both vaccine trials was around two months⁶, the vaccines are not 100% effective,⁶ and there are challenges to herd immunity as not everyone will be immunized due to underlying conditions preventing effective immunity and vaccine hesitancy.⁷ Thus, there is an ongoing need for effective COVID-19 treatments. Treatments for COVID-19 are currently limited. In Canada, the only approved treatment is Remdesivir,⁸ which is indicated for COVID-19 positive patients with pneumonia needing supplemental oxygen; however, results from studies of Remdesivir have been mixed.^{9,10} The main treatment for most hospitalized patients is supportive care including supplemental oxygen.¹¹ To date, there are no approved treatments for non-hospitalized patients diagnosed with COVID-19. The majority of research on treatments for COVID-19 has focused on hospitalized patients, while community research, aside from vaccines, is largely observational.

The use of natural health products (NHPs), including vitamins, minerals, and herbs, to treat COVID-19 infections has received attention in both the academic community and the public.^{12,13} Various NHPs have undergone observational and clinical research for a wide variety of other upper respiratory tract infections (URTIs). These trials mainly focus on the treatment of URTI symptoms, including reducing their duration and severity. Some of the most heavily researched NHPs include andrographis,^{14,15} quercetin,¹⁶ vitamin C,¹⁷⁻¹⁹ vitamin D,²⁰⁻²² and zinc,²³ each with varying effectiveness. Naturally, these NHPs present candidates for the treatment of symptoms associated with COVID-19. While there has been observational evidence to support some NHPs for the treatment of COVID-19, such as vitamin D^{24,25} and vitamin K²⁶, currently there are no published double-blind, placebo-controlled, randomized clinical trials studying NHPs and COVID-19 symptoms. Based on the above studies for COVID-19 and other similar URTIs, the nutrients vitamin C, vitamin D, vitamin K2, and zinc stand out as the most promising NHPs for the treatment of symptoms caused by COVID-19.

This project is timely as several other organizations and researchers are looking into these and other NHPs for COVID-related treatments.²⁷⁻³² With no proven treatments available for managing COVID-19 symptoms in the community, the burden on the healthcare system remains high. If a collective positive result is seen, these NHPs could provide an inexpensive, safe treatment for COVID-19 symptoms in the

community and decrease the burden on the healthcare system through reduced hospitalizations and decreased length of stay while in hospital.

2. Objectives and Hypotheses

2.1. Objectives

The overarching goal of the project is to determine if supplementation with dietary nutrients (specifically vitamin D, vitamin C, vitamin K2, and zinc) improves overall health by decreasing symptom severity and duration for outpatients diagnosed with SARS-CoV-2.

2.1.1. Primary Objective

The primary objective will be the difference in participant-reported overall health in each arm.

2.1.2. Secondary Objectives

Secondary objectives include:

1. Effect of COVID-19 on the health status of participants
2. Symptom severity of COVID-19 symptoms, including: fever, cough, shortness of breath, fatigue, headache, myalgia/arthralgia (body aches), nausea, vomiting, diarrhea, shakes/chills, congestion, and loss of taste and smell
3. Total symptom duration
4. Incidence of delayed return to usual health
5. Frequency of hospitalizations, including: ER visits, acute care admissions, and ICU admissions
6. Hospital length of stay
7. All-cause mortality

2.2. Hypothesis

We hypothesize that supplementation with vitamin D, vitamin C, vitamin K2, and zinc will increase participant-reported overall health and health status in outpatients diagnosed with SARS-CoV-2 compared to a placebo. We also hypothesize the intervention will reduce the severity and duration of common COVID-19 symptoms experienced in a community setting.

3. Methods

3.1. Study Design

This study is a double-blind, placebo-controlled, phase III randomized controlled trial powered to detect meaningful differences in the overall health and symptom severity of people with COVID-19 between the treatment and control arms. Eligible participants will be randomly assigned, using a web randomization system, in a ratio of 1:1 to one of the following groups: (1) nutrient therapy with vitamin D, vitamin C, vitamin K2, and zinc or (2) placebo. Total trial duration will be 12 weeks. Nutrients or placebo will be given for a period of 21 days following enrolment and randomization. The length of the intervention period (21 days) encompasses the most common period within which recovery occurs. The median duration of time to symptom resolution is 4-8 days from testing and yet a substantial number of people (26-47%) do not return to their usual state of health within 14-21 days.³³ Available guideline recommendations support a prolonged follow up period in order to assess patients experiencing ongoing symptomatic COVID-19 (signs and symptoms for 4-12 weeks) and those with post-COVID-19 syndrome (signs and symptoms >12 weeks).³⁴

3.2. Participants

Potential participants will be identified by clinical nursing staff at The Ottawa Hospital (TOH) who are responsible for contacting anyone who tests positive for COVID-19 at a testing centre associated with TOH. Specific screening and recruitment procedures are described in section 4.3.

3.3. Inclusion/Exclusion Criteria

3.3.1. *Inclusion criteria:*

1. Adults (≥ 18) who test positive for SARS-CoV-2 by reverse transcriptase polymerase chain reaction (RT-PCR) in an outpatient setting
2. Access to internet

3.3.2. *Exclusion criteria*

1. Symptom onset greater than 7 days prior to enrolment
2. Supplementing regularly with >500 mg vitamin C, >1000 units vitamin D, >120 mcg vitamin K (any form), or >15 mg zinc taken daily within the past month
3. Currently taking warfarin or an equivalent vitamin K antagonist anticoagulant
4. End stage chronic kidney disease
5. History of calcium oxalate kidney stones
6. Active granulomatosis (sarcoidosis, tuberculosis, lymphoma)
7. Known hypercalcemia or hypervitaminosis D

8. Currently taking either of the following antibiotics: cephalexin, tetracyclines
9. Known allergy to any investigational product, silicon dioxide, cellulose, or medium chain triglyceride oil
10. Participating in an investigational study or participation in an investigational study within the past 30 days
11. Any reason which, under the discretion of the qualified investigator or delegate, would preclude the patient from participating.

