3.5. Manufacturing & Distribution of Product

Investigational products (including active treatments and placebo) for this study will be manufactured and distributed to participants by Vitazan Herbs and Supplements Inc. Specific formulations of each study product are outlined below.

Specific Product: Vitamin D3 50,000 IU

Formulation: Capsule. Each capsule will contain 500 mg (50,000 units) cholecalciferol (vitamin D3)

Dose: One capsule on day 1 of the intervention period

Placebo Equivalent: microcrystalline cellulose capsule, 350 mg

Absolute Contraindications: history of hypervitaminosis D, hypercalcemia or sarcoidosis

Specific Product: Vitamin K2/D

Formulation: Liquid. Each 0.0285 mL drop contains 30 mcg menaquinone-7 (MK-7, vitamin K2) and 3.125 mcg (125 units) cholecalciferol (vitamin D3).

Dose: 0.114 mL (four drops) twice daily for 21 days totalling 240mcg MK-7 and 1,000 units cholecalciferol per day.

Placebo Equivalent: Medium chain triglyceride oil

Absolute Contraindications: history of hypervitaminosis D, hypercalcemia or sarcoidosis; warfarin or another vitamin K antagonist anticoagulant

Specific Product: Vitamin C/Zinc

Formulation: Capsule. Each capsule will contain 666 mg ascorbic acid (vitamin C) and 8.3 mg of zinc acetate

Dose: Three capsules three times daily for 21 days totalling 6 g ascorbic acid and 75 mg zinc acetate per day.

Placebo Equivalent: microcrystalline cellulose capsule, 350 mg

Absolute Contraindications: calcium oxalate kidney stones, end stage chronic kidney disease, cephalexin, tetracycline antibiotics

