3.6. Concomitant Medications & Stopping Rules

All concomitant medications and natural health products from enrolment to end of study (3 months) will be recorded. All information will be participant-reported. Absolute contraindications are outlined in the exclusion criteria and in section 3.5. Should a participant be placed on one of these medications or be diagnosed with one of the conditions, they will stop taking the study product. Participants may also be instructed to either temporarily or permanently discontinue the intervention if the participant does not tolerate the intervention at the discretion of study doctor or treating doctor. There are no required rescue medications for this study.

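### The limit on participants' own vitamin C, D, K and zinc ends at enrolment; during the 21-day outcome window their use is only recorded, and no analysis uses the record

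*Combined protocol and SAP*

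**What the plan says.** **At entry.** Exclusion 2 in section 3.3.2 begins "Supplementing regularly with >500 mg vitamin C" and continues with ">1000 units vitamin D, >120 mcg vitamin K (any form), or >15 mg zinc taken daily within the past month". It is the only limit on the four nutrients in the supplied text.

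**After enrolment.** Section 3.6 states "All concomitant medications and natural health products from enrolment to end of study (3 months) will be recorded", by participant report. Its stopping rule applies when a participant is put on a contraindicated drug, is diagnosed with a contraindicated condition, or does not tolerate the intervention. The consequence is that the study product stops. It does not address supplements that participants buy themselves. Table 1 lists concomitant medications, adverse events and other items at the follow-up calls, including days 7, 14 and 21, but does not mention supplements by name.

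**In the analysis.** Section 6.2.1.1 defines the primary outcome as the EQ-VAS area under the curve over the 21 intervention days. Section 6.2.2 specifies intention to treat with unadjusted t-tests. No section tabulates or otherwise uses the supplement record.

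**The concern.** Exclusion 2 must serve either to protect the contrast between arms or to limit total intake. Both purposes apply at least as strongly on days 1-21 as in the month before, yet the restriction stops at enrolment.

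The protocol makes such use plausible. Section 3.4 describes vitamins C, D and K as available as dietary supplements. The background section notes public interest in natural health products for COVID-19, and section 3.6.1 says there is no community standard of care. A participant who knows the trial's subject and may be on placebo can start these products after randomisation and still be following the supplied protocol.

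The entry wording leaves a related gap. Enrolment is allowed up to 7 days after symptom onset. Someone who began high doses a few days earlier could be read as not yet a regular user.

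What is at stake is the reading of a null result. Section 10 says a negative outcome would help patients avoid paying for a therapy that does not work. That inference needs a placebo arm largely free of the nutrients, or at least a report of how free it was.

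**Working it through.** **1. Is there a rule for days 1-21?** Set side by side:

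| Place | Period | What it does about own-supply nutrients |
|---|---|---|
| 3.3.2, exclusion 2 | month before enrolment | excludes use above the limits |
| 3.6, recording | enrolment to 3 months | records, by participant report |
| 3.6, stopping rule | while on study product | stops study product; silent on own supply |
| Table 1, calls | days 7, 14, 21 and later | concomitant medications; supplements not named |
| 6.2.2 | analysis | no use of the record |

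Section 3.6 refers to the exclusion criteria for absolute contraindications. Even if that were stretched to include exclusion 2, the result would be stopping study product, which does not keep the nutrients out of the placebo arm.

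**2. The plan's own effect size and sample size.** Section 5 gives a standardised effect of 0.3, 88 per arm, 80% power and alpha 0.05, without stating sidedness. A two-sided two-sample t-test at d = 0.3 needs about 176 per arm for 80% power; at 88 per arm the power is about 51%. The stated 88 per arm therefore does not reproduce. That is a separate matter, so both sample sizes are carried below.

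**3. Bound on dilution.** Let c be the share of placebo participants who obtain the full effect from their own supply. The documents give no value for c, so the values here are assumptions. Suppose also that own-supply use adds nothing in the active arm, that no user gains more than the full effect, and that the standard deviation is unchanged. Then

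d(c) = 0.30 × (1 − c), and the sample size needed grows by 1/(1 − c)².

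| c (assumed) | d(c) | Power, 88 per arm | Power, 176 per arm | Sample size factor |
|---|---|---|---|---|
| 0% | 0.30 | 51% | 80% | 1.00 |
| 10% | 0.27 | 43% | 71% | 1.23 |
| 20% | 0.24 | 35% | 61% | 1.56 |
| 30% | 0.21 | 28% | 50% | 2.04 |

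At each c this is the largest dilution. A user who obtains only part of the effect dilutes less.

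**The case against.** **Vitamin D.** A reader might infer that a placebo participant at the vitamin D entry limit already matches the active arm, because the drops are "0.114 mL (four drops) twice daily for 21 days totalling 240mcg MK-7 and 1,000 units cholecalciferol per day". The arithmetic for the drops is right (4 × 2 × 125 = 1,000 units), but it leaves out "Specific Product: Vitamin D3 50,000 IU", given as "One capsule on day 1 of the intervention period". Active-arm vitamin D over 21 days is 50,000 + 21 × 1,000 = 71,000 units, so the limit amounts to 21,000/71,000 = 30% of it. Section 3.4 gives the capsule the role of raising levels quickly and the daily amount that of maintaining them. An entry limit equal to the drop amount is not a contradiction.

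**Background use at entry.** Randomisation balances this in expectation. With both arms at the limit, the difference in vitamin D is (71,000 + 21,000) − 21,000 = 71,000 units, unchanged. Ratios of limit to dose therefore do not measure contamination.

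**Direction.** A reader might also infer that contamination affects only the placebo arm. Participants are blinded (section 4.5), so own-supply use may occur in both arms, and the net dilution depends on the dose response.

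**Size.** The full-effect assumption is demanding. Section 3.4 reports no effect of low vitamin D doses, and ties benefit to at least 6 g of vitamin C and 75 mg of zinc a day. On that rationale casual use would dilute much less.

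**Absence.** The consent pages and the Procedures Manual (section 4.2.2) were not available, and an instruction to participants could sit there. Exclusion 2 can also be read to cover recent daily use, and exclusion 11 leaves the investigator discretion.

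All of this stands, and it limits the claim. It does not supply a rule for days 1-21 in section 3.6 or a use for the recorded data.

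**Conclusion.** The concern holds as a gap between exclusion 2 and section 3.6. In the supplied text the sponsor's restriction on the four nutrients ends at enrolment, use during the primary outcome window is only recorded, and the record has no planned use. Own-supply use in the placebo arm can reduce the contrast and make a null result hard to interpret.

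The size is unknown. The values 0.27, 0.24 and 0.21 are the lowest the 0.30 effect would reach at assumed rates of 10%, 20% and 30%, under the assumptions stated with the calculation. They are not forecasts. The documents do not support saying that the placebo arm may match active-arm vitamin D at the entry limit, that contamination is confined to placebo, or that no instruction exists anywhere outside the supplied text.

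**What to change.** 1. Reconcile section 3.6 with exclusion 2. From consent to day 21, ask participants in both arms not to use non-study products containing vitamin C, D, K or zinc above the limits the sponsor already wrote in exclusion 2. Except products that a treating clinician recommends, consistent with section 3.6.1. If such an instruction already exists in the consent form or Procedures Manual, cite it in section 3.6 instead.
2. Clarify that exclusion 2 covers current use begun since symptom onset.
3. At the existing day 7, 14 and 21 calls, ask specifically about non-study use of the four nutrients.
4. Add to section 6.2 a table of that use by arm over days 1-21.
5. Keep every participant in the intention-to-treat analysis, including those who do not follow the request.

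The cost is a short change to the protocol and, if needed, the consent form, one question in calls already planned, and one table. A few candidates may decline or be screened out. The request and the call question help only for participants who have not yet completed the 21 days, so the change should be made early.

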3.4. Interventions

The interventions for this study will consist of dietary supplements for participants in the treatment arm and a placebo for those in the control arm. Three vitamins and one mineral will be included in the intervention for those in the treatment arm – vitamin D3, vitamin C, vitamin K2, and zinc. Upon enrolment and randomization, participants will be provided either dietary supplements or placebo by the study staff. Study interventions are to be started as soon as possible after enrolment and randomization and will continue for 21 days. Participants will be responsible for taking their doses and will be required to return all unused study product to the CHI or their local pharmacy to be properly destroyed. Phone calls will be made to participants at weeks 1, 2, 3, and 4 post-enrolment to check in and inquire about compliance and potential side effects.

All pill bottles will bear labels that comply with Health Canada Regulations. These labels will be in both official languages and contain the expiry date, storage conditions, lot number and the name and address of the manufacturer. An additional statement will be added to each label indicating that it is an investigational product to be used only by a qualified investigator, the trial's sponsor name and address, and protocol code. All study products will be packaged in sealed bottles. Participants will be instructed to store all products as indicated on the product label in a location that is out of reach of children and not to use if the seal is broken. Product accountability records will be maintained to track dispensation, returns and destruction of the study product, and will be maintained by the study staff at the Centre for Health Innovation (CHI). Product inventory will be stored as indicated on the label with daily temperature monitoring.

Information regarding all investigational products, including dosing, timing, absolute contraindications and rationale for use, is summarized below and in section 3.5.

Vitamin D: Vitamin D (cholecalciferol [vitamin D3]) is a fat-soluble vitamin that is synthesized following ultraviolet radiation to the skin, naturally occurs in a few dietary sources and is available as a dietary supplement. Cholecalciferol is the most used supplemental form of vitamin D and is the proposed form for this study. The importance of vitamin D for bone and dental health and for absorption of calcium and phosphorus are well recognized. Moderate doses of Vitamin D have been shown to reduce the duration and severity of upper respiratory tract infections,²² whereas low doses showed no effect,²² and preliminary reports show Vitamin D levels and vitamin D supplementation may reduce COVID-19 disease severity and progression.^{25,35-39} Given only 68% of Canadians have a vitamin D level of >50 nmol/L on

average,⁴⁰ a loading dose is necessary to quickly elevate levels in the average Canadian to sufficiency (≥ 75 nmol/L) and a maintenance dose is necessary to maintain these levels for the duration of the trial.

Vitamin C: Vitamin C (ascorbic acid, ascorbate) is a water-soluble vitamin that naturally occurs in many foods and is sold as a dietary supplement. It is required for the functioning of several enzymes and is important for the immune system. Reductions in ascorbate levels in people with infections, the common cold, and pneumonia have been observed and may be due to increases in reactive oxidation species during the immune response.¹⁸ A review of clinical trials and predictive models indicated that doses ≥ 6 g per day may be effective in reversing this decline and reducing common cold symptom severity and duration compared to controls.^{18,19,41} In 18 ICU patients with COVID-19 meeting ARDS criteria, 94.4% had undetectable vitamin C levels and 5.6% had low levels (2.4 mg/L), indicating an acute situational deficiency due to SARS-CoV-2 infection.⁴² A dose schedule of 2g three times daily will be used in an effort to maximize absorption as absorption decreases as the dose increases.⁴³

Zinc: Zinc is one of the most abundant essential trace elements in the human body and is required for the function of several hundred enzymes and transcription factors. Zinc has long been studied in people with the common cold for the reduction of symptom severity and duration with proposed mechanisms include inhibiting binding of the rhinovirus in the nasal mucosa,⁴⁴ inhibiting proteolysis during the rhinovirus cell cycle,⁴⁵ and inhibiting rhinovirus replication.⁴⁶ Reviews of zinc administration for common cold symptoms show doses ≥ 75 mg per day outperform doses below that threshold,^{23,47} indicating a clear target dose. Of the available forms, zinc acetate has seen the largest reduction in the common cold compared to other salts⁴⁸ and will be the formulation used in this study. Whereas many common cold studies administer zinc in a lozenge form due to its local effects in the nasal cavity, rhinorrhea is less common in patients with SARS-CoV-2.⁴⁹ Based on this and the difficulty of creating a placebo lozenge, capsule form is likely not disadvantageous and the most feasible formulation for application.

Vitamin K2: Vitamin K (menaquinone-7 [vitamin K2]) is a fat-soluble vitamin found in foods and sold as a dietary supplement. Vitamin K plays a large role in synthesizing coagulation factors in the blood, and vitamin K deficiency has been associated with uncontrolled bleeding. Vitamin K1 (phylloquinone) is an alternate form of vitamin K found in foods and supplements; however, vitamin K2 has a better absorption profile⁵⁰ and additionally plays a role in bone metabolism controlling the binding of calcium, especially in older adults, where it attenuates the rate of bone loss. Vitamin K2 has also been implicated in the risk of cardiovascular disease and type-2 diabetes, which are common among people with severe COVID-19. Menaquinone-7 (MK-7) may confer protection for pulmonary elastic fibers against calcification through MK-7-dependent matrix Gla protein activity.⁵¹ Coagulopathy coupled with reduced vitamin K status has been seen in patients with severe COVID-19 and correlates with decreased survival,^{26,52,53} thus our goal will be to achieve and maintain sufficient levels to correct deficiencies that may be associated with poorer outcomes. While the recommended daily allowance (RDA) is 90-120 micrograms,⁵⁴ 240 micrograms will be administered in order to ensure the majority of participants, with a range of vitamin K statuses, achieve sufficiency within the short period of time. Doses of up to 360 micrograms of MK-7 for 12 weeks have been found to be well tolerated and safe,⁵⁵ with predominantly extrahepatic effects.⁵¹ Although other forms of vitamin K2 can be used, such as menaquinone-4, MK-7 was chosen as it has superior

bioavailability and clinical efficacy to this and other forms of vitamin K2.^{54,56-58} Vitamin K is contraindicated with vitamin K antagonist anticoagulants, such as Warfarin. Although anticoagulant therapy is common among hospitalized patients with COVID-19, TOH administers low molecular weight heparins or heparin as anticoagulants; thus, there is no potential for any interactions. Vitamin K2 additionally has a strong safety profile; a review of recent literature found there were no adverse effects related to blood coagulation for people taking MK-7 at doses up to 6 mcg/kg/day in adults.⁵⁵

